3.1.2 Treatment at progression

Since progression marks the achievement of the primary endpoint, the treatment upon progression is left to investigator clinical judgment.

In the control arm (observation) crossover to regorafenib plus durvalumab is allowed.

Table 4. Contribution of nine different events to the definition of six endpoints in adjuvant studies with cancer patients

Event	Endpoint ^a					
	DFS	RFS	TTR	TTF	CSS	OS
Loco-regional recurrence	E	E	E	E	I	I
Distant metastases	E	E	E	E	I	I
Second primary, same cancer	E	I	I	E	I	I
Second primary, other cancer	E	I	I	E	I	I
Death from same cancer	E	E	E	E	E	E
Death from other cancer	E	E	C	E	C	E
Non-cancer-related death	E	E	C	C	C	E
Treatment-related death	E	E	C	E	C	E
Loss to follow-up	C	C	C	C	C	C

(Consensus agreement, from: Punt, 2007).

^a DFS = disease-free survival; RFS = relapse-free survival; TTR = time to recurrence; TTF = time to treatment failure; CSS = cancer specific survival; OS = overall survival; **E** = event; **C** = censor; **I** = ignore

To the purpose of this trial a **loco-regional recurrence or systemic recurrence** is defined as follows:

CT positive or CT uncertain with elevated CEA and positive PET scan.

3.2 Secondary Objectives

The secondary objectives of this study are:

- to assess the short-term effects of adjuvant regorafenib plus durvalumab on DFS
- to assess the effect of adjuvant regorafenib plus durvalumab on all causes mortality.
- to investigate potential correlation between molecular and biological markers and survival outcomes(progression and death) in patients treated with adjuvant regorafenib plus durvalumab.
- to assess toxicity correlated to study treatment
- to assess the treatment compliance

3.2.1 Secondary Endpoints

The secondary endpoints are:

- 18 months Disease-Free Survival (DFS)
- Overall Survival (OS)
- Compliance to the experimental treatment.

3.2.2 Exploratory Objectives

- Correlation between ctDNA and survival outcomes (progression and death) in patients treated with adjuvant regorafenib plus durvalumab.
- Explore the potential prognostic and predictive value of Next-generation sequencing analyses, Tumour DNA methylation analyses, Gene expression analyses, CMS subgrouping analyses, Immune signature analyses and the correlation with the survival outcomes in mCRC NED patients enrolled in this trial.

3.3 Endpoints definition

3.3.1 Disease-free survival

The primary study endpoint is DFS as defined in Section 3.1.1 and computed for each patient from the day of randomization to the day of occurrence of first event

of interest or last follow up clinical examination. If no event (relapse or death) has been observed, the patient is censored at the date of the last follow up.

Patients who discontinue treatment prior to documented disease relapse including those who initiate non-protocol therapy prior to relapse, will be followed up for disease progression and death and will be censored at the time of therapy change.

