Tumor imaging/ response assessments ^c	X	X		X
Hematology ^d	X	X		X
Chemistry ^d	X	X		X
Biomarkers ^d	X	X		X
AEs assessments	X	X	X	X
Survival and anti-cancer therapy			X	X

Abbreviation: CBC: cell blood count; RBC: red blood cell; WBC: White blood cell; aPTT: activated partial thromboplastin time; PT: prothrombin time; INR: international normalized ratio; AST: Aspartate aminotransferase; ALT: alanine aminotransferase; LDH: Lactate dehydrogenase; β -hCG: beta-human chorionic gonadotropin; Na: sodium; K: potassium; Cl: chloride; Mg: magnesium; Ca: calcium; P: phosphate; CEA: Carcinoembryonic antigen; Ca 19-9: Carbohydrate antigen 19-9; ECOG PS: Eastern Cooperative Oncology Group Performance Status; ECG: electrocardiogram; AEs: adverse events

a) Vital signs and Physical examination

Patients will have a complete physical exam to include an examination of major body systems and an assessment for emergent toxicities or changes from prior visits. Limited physical examination should be performed symptom-directed.

Examinations will be conducted by a physician, trained physician's assistant, or nurse practitioner, as acceptable according to local regulation.

Vital signs include: blood pressure and heart rate, body temperature, respiratory rate.

b) Electrocardiogram (ECG)

Perform a 12-lead resting electrocardiogram (ECG) before the beginning of the treatment, at the end-of-treatment and if clinically indicated. Patients should be in a supine position for at least 10 min before recording. ECG tracings will be reviewed by a qualified physician for assessment of QT interval as well as signs of qualitative abnormalities, including evaluation of rhythm, ST segment morphology, T wave morphology, and presence/absence of U wave.

The original ECG tracing will be maintained in the source documentation of each patient.

c) Tumor imaging/ response assessments

Including computed tomography (CT) scan / magnetic resonance imaging (MRI) / PET scan. The same radiographic procedure should be used throughout the study for each patient.

Tumor assessment should be performed every 12 weeks \pm 1 week for the first year (relative to the date of randomization), every 16 \pm 1 week in the second year and then every 24 weeks \pm 1 week thereafter until RECIST 1.1-defined radiological PD or death (whichever comes first).

d) Local laboratory assessments will include the following:

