6.4 Withdrawal of patients from study treatment and/or study

6.4.1 Permanent discontinuation of Durvalumab or Regorafenib

Discontinuation of study treatment, for any reason, does not impact the patient's participation in the study. A patient who decides to discontinue IP will always be asked about the reason(s) for discontinuation and the presence of any AE. The patient should continue attending subsequent study visits, and data collection should continue according to the study protocol. If the patient does not agree to continue in-person study visits, a modified follow-up must be arranged to ensure the collection of endpoints and safety information. This follow-up could be a telephone contact with the patient, a contact with a relative or treating physician, or information from medical records. The approach taken should be recorded in the medical records. A patient that agrees to modify follow-up is not considered to have withdrawn consent or to have withdrawn from the study.

Patients who are permanently discontinued from further receipt of IP, regardless of the reason, will be identified as having permanently discontinued treatment. Patients who are permanently discontinued will enter follow-up (see the SoAs).

Patients who permanently discontinue drug for reasons other than objective RECIST disease progression should continue to have RECIST scans performed every 12 weeks \pm 1 week for the first year (relative to the date of randomization), and then every 16 weeks \pm 1 week in the second year and then every 24 weeks \pm 1 week thereafter until RECIST 1.1-defined radiological PD or death (whichever comes first) as defined the SoAs.

If a patient is discontinued for RECIST 1.1-defined progression, then the patient should have 1 additional follow-up scan performed preferably at the next (and no later than the next) scheduled imaging visit, and no less than 4 weeks after the prior assessment of PD.

All patients will be followed for survival until the end of the study.

Patients who decline to return to the site for evaluations should be contacted by telephone as indicated in the SoAs as an alternative.

Patients who have permanently discontinued from further receipt of IP will need to be discontinued from the IVRS/IWRS.

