- and/or additional new unequivocal lesions at the confirmatory scan time-point.

NOTE: In order to have confirmed objective disease progression, there should be two consecutive assessments meeting the PD definition: the first PD by RECIST 1.1 and the second PD using the confirmation of progression criteria (above). If the first assessment fulfilling the PD definition by RECIST 1.1 is not confirmed, continue with assessments until the next PD by RECIST 1.1, which in turn will need its own immediate subsequent confirmation scan. In the absence of significant clinical deterioration, treatment with study drug may continue between the initial assessment of progression and the scan to confirm progression.

If the confirmation scan confirms progression, then the date of the prior scan with PD should be declared as the date of progression.

If progression is not confirmed, in the absence of significant clinical deterioration, then the patient should continue study drug and on-treatment assessments until the next PD which will also require a follow-up confirmation scan. If the first PD is not confirmed by the immediate next scan, then the Investigator should not change the PD assessment of the first scan.

If a patient discontinues treatment (and/or receives a subsequent anticancer therapy) prior to radiologic progression, then the patient should still continue to be followed until confirmed objective disease progression.

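### Section 3.3.1 gives three DFS censoring dates that disagree, and none is the last adequate disease assessment

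*Combined protocol and SAP*

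**What the plan says.** Section 3.3.1 contains three statements on when DFS time ends for a patient without an event:

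- DFS is computed to the first event or the "last follow up clinical examination".
- If no relapse or death is seen, "the patient is censored at the date of the last follow up".
- Patients who stop treatment before relapse, including those who start non-protocol therapy, are followed for progression and death and "will be censored at the time of therapy change".

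The OS definition in Section 3.3.2 uses nearly the same words as the second statement.

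Section 6.4.1 deals with patients who stop study drug: "If the patient does not agree to continue in-person study visits, a modified follow-up must be arranged to ensure the collection of endpoints". Safety data are gathered in the same way. It continues: "This follow-up could be a telephone contact with the patient, a contact with a relative or treating physician, or information from medical records". It also says that those who stop for reasons other than progression "should continue to have RECIST scans performed every 12 weeks" in the first year and at longer intervals later. Section 8.2.3.1 adds that if a patient stops treatment before radiologic progression, "then the patient should still continue to be followed until confirmed objective disease progression". Footnote c to the schedule tables sets the imaging calendar for both arms: "Tumor assessment should be performed every 12 weeks" in year 1, every 16 weeks in year 2, then every 24 weeks. Section 8.1.4, however, leaves imaging during follow-up to the investigator's choice.

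**The concern.** Relapse is found by imaging, CEA or clinical signs (Sections 3.1.1 and 8.2.3.1). Time after the last such assessment is not evidence that the patient is disease-free. A censoring date that can lie well beyond it credits event-free time that was not observed.

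This matters more when it happens in one arm. During the adjuvant phase only the experimental arm has study drug to stop, so the remote route in Section 6.4.1 arises there. For OS, a telephone contact plainly counts as follow-up (Section 8.1.4 uses one for that purpose). Section 6.4.2 has survival status re-checked to support both DFS and OS. Nothing gives the phrase a narrower meaning for DFS, so an analyst could apply the OS convention to the primary endpoint. The choice would then be made at analysis, in an open-label trial, and could move the primary hazard ratio.

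**Working it through.** **1. The plan's own figures.** Events for HR 0.60, two-sided 0.05, 90% power, 1:1: 4 × (1.960 + 1.282)² / (ln 0.60)² = 42.0 / 0.261 = 161.1, or 162 as an even number. The plan says 164, which gives 90.5% power. With exponential DFS, medians of 6 and 10 months, 24 months of accrual and 24 more of follow-up, the event probabilities are 0.979 and 0.908, mean 0.943. So 172 patients give 172 × 0.943 = 162 events, and 172 / 0.95 = 181.1, rounded up to 182. The sample size reproduces, and the point does not turn on it.

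**2. The three dates applied to one patient.** Take a treated patient scanned at week 12 who stops study drug at the week 16 visit. (Section 8.1.3 needs no repeat scan within 28 days.) The patient starts no other therapy, declines further visits and is reached by telephone until data cut-off with no relapse reported.

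| Rule | Censoring date |
|---|---|
| Last follow-up clinical examination | Week 16 |
| Last follow-up, read as for OS | Data cut-off |
| Therapy change, read as treatment stop | Week 16 |
| Therapy change, read as start of another therapy | None defined |
| Last scan (not in the plan) | Week 12 |

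**3. Size if remote contact counts.** Inputs from the documents: 91 patients per arm, control median 6 months, accrual and follow-up as above, the footnote c imaging schedule with its ±1 week window, Cox hazard ratio and log-rank test. Inputs assumed, because the documents do not give them:

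- q, the share of treated patients set to move to remote follow-up;
- d, the share of these whose relapse is still captured on time;
- stopping time uniform over 0–12 months and unrelated to prognosis;
- exponential DFS;
- median 30 months from relapse to death, with deaths counted as DFS events.

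A patient who relapses before the switch never becomes remote, so the number actually remote is below q × 91. At q = 10%, 0.10 × 91 = 9.1 patients are set to switch, but censoring them at the stop loses only 176.5 − 171.1 = 5.4 events.

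True HR 1.00, last-contact censoring, 5,000 trials per setting. Cells show the HR and the false-positive rate in favour of treatment (nominal 2.5%):

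| q | d = 0 | d = 50% | d = 80% |
|---|---|---|---|
| 5% | 0.94 (6%) | 0.97 (4%) | 0.99 (3%) |
| 10% | 0.88 (12%) | 0.93 (7%) | 0.97 (4%) |
| 20% | 0.79 (34%) | 0.88 (12%) | 0.95 (6%) |

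In the same settings, censoring at the last scan gives HR 1.00–1.02, and censoring at the treatment stop gives 1.00–1.01. Both have false-positive rates of 2–3%. With a true HR of 0.60, q = 10% and d = 0, the estimates are 0.545 (last contact), 0.61 (last scan) and 0.60 (treatment stop). Monte Carlo error on the rates is about 0.2–0.7 percentage points.

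**4. Deaths after an assessment gap.** The last-scan result in step 3 does not count deaths of remote patients after their last scan. In a coarser run (2,000 trials per setting, scans exactly on schedule) at q = 10%, d = 0, the HR was 0.90 with last contact, 0.98 with last-scan censoring if those deaths still counted, and 1.00 if they did not. The rule therefore has to say how such deaths are treated.

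**5. Visit frequency.** On the clinical-examination reading, treated patients are seen monthly between 12-weekly scans, while control visits coincide with scans. The unscanned gap is at most about 12 − 4 = 8 weeks. With 5–15% dropout this shifts the HR by less than 1%.

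**The case against.** A reader might infer that the plan censors DFS at the last contact, so that treated patients collect time nobody checked and DFS is biased towards treatment. The documents do not support that as a flat statement, for four reasons.

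- The DFS definition never mentions contact. The sentence before the censoring rule names a clinical examination, and the natural reading is that the rule refers back to it. A telephone call is not an examination.
- The therapy-change sentence covers the very patients who can use the remote route. Read as censoring at treatment stop, it removes the bias.
- Modified follow-up is required in order to collect endpoints, scans stay on schedule, and Section 8.1.3 includes imaging at the end of treatment. A treating physician or medical records can supply results, and Section 8 has standard-of-care scans and marker results entered in the eCRF.
- The size depends on two shares that the documents do not give. With 80% capture and 5–10% remote it is only 0.97–0.99.

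A fifth objection concerns the repair. Clinical signs and two CEA rises are DFS events without a scan (Section 3.1.1), so censoring strictly at the last scan discards valid assessments.

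All of this stands as a limit on the claim, but none of it settles the rule. The operative censoring sentence drops the examination and matches the OS wording, and an examination is in any case not a tumour assessment. The therapy-change sentence gives no date for a patient who stops and starts nothing. If it does mean treatment stop, it sits badly with the follow-up for progression in the same sentence, with continued scanning, and with the ITT analysis in Sections 5.1 and 5.2.1. It may also be informative. Patients who decline visits are the least likely to be scanned, whatever the schedule requires.

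**Conclusion.** The point holds as a defect of definition with a conditional bias. It is certain that Section 3.3.1 gives three dates that do not agree, that none is the last adequate disease assessment, and that nothing says how missed assessments are handled. Bias towards treatment follows only if remote contacts count as DFS follow-up and some relapses go uncaptured. With no true effect, the HR is then about 0.94 to 0.99 with 5% of treated patients set to switch, and 0.88 to 0.97 with 10%, running from no capture to 80% capture. These are scenarios and not predictions: they assume exponential DFS, switching spread over 0–12 months and stopping unrelated to prognosis. If these patients are censored when treatment stops, this bias is absent (HR 1.00–1.01). The visit-frequency asymmetry alone is negligible. The change should be made because it is cheap and removes a choice that could otherwise be made after the results are known.

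**What to change.** In Section 3.3.1, replace the three statements with one rule:

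- Censor patients without an event at the last adequate disease assessment for the protocol's own DFS events, with protocol imaging as the main rule, or at randomisation if there is none. Add a sensitivity analysis that uses the last CEA or clinical examination.
- Keep the last-contact or survival-status date for OS only.
- State how a relapse or death after missed assessments is dated and whether it counts.
- Reconcile the therapy-change sentence with this rule and with the ITT analysis. If that censoring is wanted, it can be a labelled sensitivity analysis.
- Report time from last assessment to data cut-off by arm.
- Align the imaging statement in Section 8.1.4 with footnote c, so that an adequate assessment refers to one schedule.

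The cost is a short paragraph, agreed before any comparison of arms. Scan and CEA data already go to the eCRF (Sections 8, 8.2.3.2 and 8.2.3.3), and the sample size does not change. The downside is slightly less follow-up time for some censored patients.

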3.3.2 Overall survival

Defined as time from the date of randomization until death from any cause. If no event (death) has been observed, the patient is censored at the date of last follow up.

3.3.3 Toxicity

Toxicity / adverse events classified according to NCI CTCAE version 5.0 [61] .

3.3.4 Compliance to the experimental treatment

Defined as the ratio between the actual and expected number of Durvalumab+Regorafenib administrations in each patient.

4 INVESTIGATIONAL PLAN

4.1 Description and Justification of the Trial Design and Plan

This project is a randomized, open-label, multicenter study. All eligible patients, after completion of locoregional treatment to render them disease free, will be randomized to experimental treatment (adjuvant regorafenib plus durvalumab) or no further treatment (observation). Randomization is 1:1. Patients randomized to the experimental arm will receive up to 1 year of regorafenib + durvalumab. Patients randomized to the control arm will receive no further treatment. Patients in the control arm will be offered the possibility to crossover to regorafenib plus durvalumab upon relapse.

4.1.1 Justification of a no treatment control group

The use of an untreated control group (i.e., no further treatment) is acceptable when patients in the control group are managed as per SoC, and patients are informed of the possibility of being randomized to no further treatment.

Standard of care “treatment” for CRC patients after resection surgery and chemotherapy is observation. The possibility of randomization to no further treatment will be clearly documented in the Informed Consent Form (ICF).

4.1.2 Justification of an open label design

The primary study endpoint is Disease-Free Survival (DFS) (Section 3.1). The open label design (lack of masking) is justified by the need of up to 1-year placebo injections and placebo pills, which are not felt ethically justifiable.

4.1.3 Justification of DFS as primary study endpoint

The choice of DFS as the primary study endpoint is justified by

- a) the intrinsic clinical relevance of living without relapse and,
- b) the demonstration of its validity as a surrogate endpoint of overall survival (OS)[62].

4.3 Study plan

Approximately 182 patients, >18 years of age, with Stage IV CRC and no evidence of disease (NED) will be enrolled. Randomization will be 1:1.

Prior to enrolment, all patients will have received standard of care (SoC) treatment for Stage IV CRC (locoregional), and will have to be NED.

Treatment schedules and safety and efficacy assessments will be the same for all patients, regardless of treatment group.

All patients will undergo assessments (Section 6.2) to confirm compliance with inclusion and exclusion criteria, after that they will sign informed consent. Patients who will be randomized to the experimental treatment group will receive up to 1 year of regorafenib plus durvalumab.

Run-in phase: The combination of an immune-checkpoint inhibitor plus TKI anti-angiogenic agents has been extensively investigated in several trials (phase II and III) in different types of tumors, with no evidence of new safety signals. Although specific data are not available on the combination of durvalumab and regorafenib, we would not expect major toxicity issues.

Therefore, a run-in phase will be conducted on the first 4 patients randomized to the experimental arm using a starting dose of 60 mg/die of Regorafenib (and fixed 1500 mg of Durvalumab), to be escalated after 2 months to 90 mg/die if < 2 patients report serious adverse events (SAE). If Regorafenib 90 mg/die is well tolerated for other 2 months (< 2 patients with SAE) the run-in phase will be closed with the dose of 90 mg/die. In case of > 2 patients report SAE with 90 mg/die, additional 4 patients will be enrolled and treated with the same dose of Regorafenib (90 mg/die) and if < 2 of them report SAE the run-in will be closed at 90 mg/die. Conversely, if > 2 patients report SAE the dose of Regorafenib will be reduced again to 60 mg/die and the run-in will be closed with Regorafenib 60 mg/die.

If during the first part of the run-in > 2 patients report SAE with Regorafenib 60 mg/die, additional 4 patients will be treated with Regorafenib 30 mg/die for 2 months and, in case of > 2 patients with SAE, the trial will be revised. In case of good tolerance of Regorafenib 30 mg/die (< 2 patients with SAE), additional 4 patients will be enrolled and treated with Regorafenib 60 mg/die: if > 2 patients will report SAE the run-in phase will be closed with Regorafenib 30 mg/die, instead if Regorafenib 60 mg/die will be well tolerated (< 2 SAE) this will be the final dose of the run-in phase.

(see Flowchart in Appendix 4)

The first regorafenib plus durvalumab cycle will be administered on Day 1.

The timing of visits, assessments and procedures is detailed in Section 8 and in Table 1, Table 2, and Table 3, respectively.

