A further consideration is that some patients treated with 80 mg of regorafenib still require dose reductions and with 40 mg tablets, a 50% dose reduction is drastic and not considered usual practice.

Based on PK and PD data from the phase I dose escalation trial (11650), regorafenib exposure in the range expected for a dose of 40 mg had less of an impact on levels of sVEGFR2 as compared to exposure associated with doses \geq 60 mg. Since VEGFR inhibition is one of the proposed mechanisms for the beneficial effect of regorafenib and PD-(L)1 inhibitor combination therapy, this is relevant to consider.

Dosing regorafenib in combination using a lower strength tablet would allow flexibility to achieve a starting dose between 80 and 120 mg and have a more gradual dose reduction if needed.

In order to provide maximum flexibility to attain an optimal dose, with the current information, 30 mg tablets are optimal. A starting dose of 90 mg (3 tabs) in combination therapy is recommended. Should an initial dose reduction be required, the first dose reduction would be to 60 mg (2 tablets), which is a more conventional 30% reduction and is also expected to provide regorafenib exposure in a pharmacologically active range.

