7.1 Treatment Administered

Patients randomized and assigned to experimental arm will receive Regorafenib + durvalumab. Treatment will begin only after the patient has been randomized to the Treatment Group. Regorafenib 90 mg will be administered orally once daily for the first 21 days of each 28-day cycle, up to 1 year. Durvalumab (1500mg q4W IV infusion) will be administered every four weeks up to 1 year.

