7.1.1 Run-in phase

Run-in phase: The combination of an immune-checkpoint inhibitor plus TKI anti-angiogenic agents has been extensively investigated in several trials (phase II and III) in different types of tumors, with no evidence of new safety signals. Although specific data are not available on the combination of durvalumab and regorafenib, we would not expect major toxicity issues.

Therefore, a run-in phase will be conducted on the first 4 patients randomized to the experimental arm using a starting dose of 60 mg/die of Regorafenib (and fixed 1500 mg of Durvalumab), to be escalated after 2 months to 90 mg/die if < 2 patients report serious adverse events (SAE). If Regorafenib 90 mg/die is well tolerated for other 2 months (< 2 patients with SAE) the run-in phase will be closed with the dose of 90 mg/die. In case of > 2 patients report SAE with 90 mg/die, additional 4 patients will be enrolled and treated with the same dose of Regorafenib (90 mg/die) and if < 2 of them report SAE the run-in will be closed at 90 mg/die. Conversely, if > 2 patients report SAE the dose of Regorafenib will be reduced again to 60 mg/die and the run-in will be closed with Regorafenib 60 mg/die.

If during the first part of the run-in > 2 patients report SAE with Regorafenib 60 mg/die, additional 4 patients will be treated with Regorafenib 30 mg/die for 2 months and, in case of > 2 patients with SAE, the trial will be revised. In case of good tolerance of Regorafenib 30 mg/die (< 2 patients with SAE), additional 4 patients will be enrolled and treated with Regorafenib 60 mg/die: if > 2 patients will report SAE the run-in phase will be closed with Regorafenib 30 mg/die, instead if Regorafenib 60 mg/die will be well tolerated (< 2 SAE) this will be the final dose of the run-in phase.

(see Flowchart in Appendix 4)

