9.1.3 Serious Adverse Event (SAEs)

A SAE is any experience that suggests a significant hazard, contraindication, side effect or precaution. It is any AE that at any dose fulfils at least one of the following criteria:

- ✓ is fatal (results in death)¹ ;
- ✓ is Life-Threatening² ;
- ✓ required in-patient hospitalization or prolongation of existing hospitalization;
- ✓ results in persistent or significant disability/incapacity;
- ✓ is a congenital anomaly/birth defect;
- ✓ is medically significant or requires intervention to prevent one or other of the outcomes listed above. Medical or scientific judgment should be exercised in deciding whether expedited reporting is appropriate in this situation. Examples of medically important events are intensive treatment in an emergency room or at home for allergic bronchospasm, blood dyscrasias, or convulsions that do not result in hospitalizations; or development of drug dependency or drug abuse.

Adverse Events (AEs) for malignant tumours reported during a study should generally be assessed as Serious AEs. If no other seriousness criteria apply, the 'Important Medical Event' criterion should be used. In certain situations, however, medical judgement on an individual event basis should be applied to clarify that the malignant tumour event should be assessed and reported as a Non-Serious AE. For example, if the tumour is included as medical history and progression

¹ Death is an outcome, not an event. The term sudden death should be used only when the cause is of a cardiac origin as per standard definition. The terms death and sudden death are clearly distinct and must not be used interchangeably.

² the term "Life-Threatening" refers to an event in which the patient was at immediate risk of death at the time of the event; it does not refer to an event which could hypothetically have caused a death if had it been more severe

occurs during the study, but the progression does not change treatment and/or prognosis of the malignant tumour, the AE may not fulfill the attributes for being assessed as Serious, although reporting of the progression of the malignant tumor as an AE is valid and should occur. Also, some types of malignant tumours, which do not spread remotely after a routine treatment that does not require hospitalization, may be assessed as Non-Serious; examples include Stage 1 basal cell carcinoma and Stage 1A1 cervical cancer removed via cone biopsy.

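### Run-in: after SAEs in 3 or 4 of 4 patients at 90 mg, the dose can still be accepted on four new patients alone, although 60 mg has just been cleared and exactly 2 of 4 has no assigned action

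*Combined protocol and SAP*

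**What the plan says.** The Synopsis, 4.3 and 7.1.1 give the same rule. The first four patients in the experimental arm start at 60 mg, "to be escalated after 2 months to 90 mg/die" if fewer than 2 have an SAE. If fewer than 2 have an SAE over the next 2 months, the run-in closes at 90 mg. If more than 2 do, "additional 4 patients will be enrolled and treated with the same dose of Regorafenib (90 mg/die"), and if fewer than 2 "of them report SAE the run-in will be closed at 90 mg/die". If more than 2 of the new four have an SAE, the run-in closes at 60 mg.

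If more than 2 of the first four have an SAE at 60 mg, four patients receive 30 mg. If that is tolerated, "additional 4 patients will be enrolled and treated with Regorafenib 60 mg/die". With fewer than 2 SAEs in that cohort, "this will be the final dose of the run-in phase".

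Every threshold is either fewer than 2 or more than 2. No visible sentence pools two cohorts at one dose. The flowchart in Appendix 4 is not visible in the copy reviewed. The re-test cohorts have no stated observation window; 2 months, as at the other stages, is the natural reading.

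**The concern.** The acceptance test at 90 mg refers only to the new four patients. The 3 or 4 SAE patients who caused the re-test are not in the count that decides.

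The order of responses is also odd. With 3 or 4 of 4 affected at 90 mg, the protocol holds a cleared lower dose, yet exposes four more patients to the dose that failed. The milder result, exactly 2 of 4, has no assigned action. In the 60 mg branch, by contrast, failure leads first to a lower dose.

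The run-in sets the regorafenib dose for the experimental arm. Section 4.3 says that specific data on this combination are lacking, the patients have no evidence of disease, and the comparator is observation. Eight patients are few, so a rule that decides on four of them discards much of what the run-in can teach.

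**Working it through.** The plan states no operating characteristics for the run-in, so there is no figure to reproduce.

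**Inputs.** From 4.3: cohorts of 4; pass = 0 or 1 with an SAE; fail = 3 or 4; 2 is unassigned. Assumed: a per-patient SAE probability p within each window of 0.1 to 0.7, because the documents give no SAE rate for the combination, and independence of patients and stages.

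**Step 1, no rate needed.** The accepted-on-re-test patterns are 3+0, 3+1, 4+0 and 4+1. That is 3, 4 or 5 of 8 patients with an SAE (37.5% to 62.5%).

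**Step 2, chance of the path once 90 mg is tested.** With X ~ Binomial(4, p), let L = P(X ≤ 1), E = P(X = 2), G = P(X ≥ 3). Failing and then being accepted has probability G × L. At p = 0.3: 0.084 × 0.652 = 0.055.

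| p | L | E | G | G × L |
|---|---|---|---|---|
| 0.1 | .948 | .049 | .004 | 0.4% |
| 0.2 | .819 | .154 | .027 | 2% |
| 0.3 | .652 | .265 | .084 | 5% |
| 0.4 | .475 | .346 | .179 | 9% |
| 0.5 | .312 | .375 | .312 | 10% |
| 0.6 | .179 | .346 | .475 | 9% |
| 0.7 | .084 | .265 | .652 | 5% |

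The maximum is 9.8%, at p = 0.5. Once the first 90 mg cohort has failed, acceptance has probability L: 65%, 48%, 31% and 18% at p = 0.3, 0.4, 0.5 and 0.6.

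**Step 3, unconditional chance.** 90 mg is tested only if 60 mg passes.
- Same rate at 60 mg: L × G × L, at most 4.1% (near p = 0.38).
- Half the rate at 60 mg: L(p/2) × G(p) × L(p) = 0.3, 2, 5, 7, 7, 6, 3% at p = 0.1 to 0.7.

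**Step 4, unequal cohorts.** The first 90 mg cohort is the escalated 60 mg cohort, so its rate may differ from that of the new four. Using G(p1) × L(p2), once 90 mg is tested: rates 0.3 then 0.2 give 7%; 0.5 then 0.3 give 20%.

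**Step 5, the rule as written against a pooled rule, once 60 mg is cleared.** As written: close at 90 mg = L + G × L; close at 60 mg = G × G; no action = E + G × E. Pooled example: close at 60 mg after 3 or 4 of 4; after exactly 2, add four and accept 90 mg only at 2/8 or fewer, so close at 90 mg = L + E × (1 − p)^4. Reading the failure limit as 2 or more: close at 90 mg = L + (1 − L) × L.

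| p | As written: 90 mg | As written: 60 mg | As written: no action | Limit read as 2 or more: 90 mg | Pooled 2/8: 90 mg |
|---|---|---|---|---|---|
| 0.1 | 95% | 0% | 5% | 99.7% | 98% |
| 0.2 | 84% | 0% | 16% | 97% | 88% |
| 0.3 | 71% | 1% | 29% | 88% | 72% |
| 0.4 | 56% | 3% | 41% | 73% | 52% |
| 0.5 | 41% | 10% | 49% | 53% | 34% |
| 0.6 | 26% | 23% | 51% | 33% | 19% |
| 0.7 | 14% | 42% | 44% | 16% | 9% |

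From unrounded values, the pooled example closes at 90 mg 1 to 4 points more often than the rule as written at p = 0.1 to 0.3, and 4 to 8 points less often at 0.4 to 0.7. Against the 2-or-more reading it is 2, 9, 16, 20, 19, 14 and 7 points less often.

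**Step 6, 60 mg branch.** Given a tolerated 30 mg cohort, failure and later acceptance of 60 mg again has probability G × L. If all eight count with a limit of 3/8, only the pattern 3 then 0 passes: 1.8%, 2.0%, 1.6% and 0.9% at p = 0.3, 0.4, 0.5 and 0.6. With a limit of 2/8, no re-test could succeed.

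**The case against.** A re-test can be defended. The trigger is any SAE, whatever its cause: 9.1.3 says "It is any AE that at any dose fulfils at least one of the following criteria", and relatedness is not among the criteria. Four patients give a noisy signal. The second 90 mg cohort also resembles the main trial more closely, since under 7.1 "Regorafenib 90 mg will be administered orally once daily for the first 21 days" of each cycle, whereas the first cohort reached 90 mg after 2 months at 60 mg. This stands as a reason to give the second cohort weight. It does not justify giving the first none, and it does not apply to the 60 mg re-test, where both cohorts start at 60 mg.

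Safeguards exist: regorafenib reductions by toxicity grade (7.5.1), SAE review that can modify or suspend the study (9.9) and a data-monitoring committee (4.2). They limit harm, but the run-in text ties none of them to the dose decision.

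Much of the benefit of a pooled rule comes from filling the exactly-2 gap. At p = 0.3 that outcome has probability 26.5% at the first 90 mg stage, against 5.5% for the re-test path. That is correct, and it is why the two belong in one redraft.

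A reader might infer that the protocol ignores the first cohort. It does not: that cohort triggers the re-test, and each SAE is reviewed. A reader might also infer that failure at 60 mg should always end the run-in at 30 mg. The documents do not support that as a requirement. Section 2.11 reports that "regorafenib exposure in the range expected for a dose of 40 mg had less of an impact on levels of sVEGFR2" than exposure at 60 mg or more, so closing at 30 mg may cost activity.

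**Conclusion.** The point holds. On the visible text, 90 mg can be cleared with SAEs in 3/8 to 5/8 of the patients treated at it, because the acceptance count leaves out the cohort that failed. That needs no assumed rate. The frequencies do: they rest on assumed SAE rates and independence, and they are low. A reader might infer that the rule is likely to select a toxic dose; the figures do not show that.

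The defect matters because the response is out of order and the repair is cheap. It is of minor to moderate severity. Confidence is moderate, because the Appendix 4 flowchart could not be checked, although the three text versions agree.

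**What to change.** Amend the Synopsis, 4.3 and 7.1.1 together, and align Appendix 4:

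- **More than 2 of 4 at 90 mg:** close at 60 mg, which has been cleared.
- **Exactly 2 of 4 at 90 mg:** add four patients at 90 mg, observe them for 2 months, and decide on all eight. Fix the limit in advance with the data-monitoring committee, below 3/8 (for example at most 2/8). If it is exceeded, close at 60 mg.
- **60 mg branch:** the re-test after a tolerated 30 mg cohort may stay if the sponsor wishes, but decide on all eight patients treated at 60 mg, with a limit agreed with the committee. That limit must be at least 3/8 for a re-test to be able to succeed. Automatic closure at 30 mg is a trade-off and is not required.
- Assign an action to exactly 2 of 4 at the 60 mg and 30 mg stages too.

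Cost: an amendment with ethics review (10.1) and a limit to agree. No more than eight patients are treated at 90 mg, as now. The downside is reduced access to 90 mg if the sponsor meant the failure limit as 2 or more: up to 20 percentage points less often with the 2/8 example.
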